Intervention: Patients aged 18 years or older who develop new-onset atrial fibrillation in the setting of severe sepsis or septic shock and in whom the medical team deems appropriate to initiate amiodarone therapy in will be considered for study inclusion. All patients will receive a 150 mg intravenous (IV) bolus dose of amiodarone, followed immediately by a continuous infusion of 1 mg/min for the first six hours, with a recommended reduction to 0.5 mg/min subsequently. Conversion from IV to oral (PO) amiodarone will occur based on patient hemodynamic stability and physician/pharmacist discretion. Patients will be randomized to receive amiodarone at a full loading dose (\geq 5g IV or \geq 10g PO +/- 20%) or a partial loading dose (<4g IV or < 8g PO). The assigned total loading dose will include all IV and PO amiodarone administered within 7 days from initiation of amiodarone. All doses will be compared in total PO amount (accounting for 50% bioavailability of PO versus IV amiodarone). The primary attending or fellow physician may over-ride randomization if the patient's amiodarone dose if the patient's severity of illness warrants a duration that differs from that assigned during randomization. In the full loading dose group, discontinuation of amiodarone will be at the discretion of the physician/pharmacists, after the pre-determined randomization loading dose has been provided.

Management Components: Facilities to be used throughout the project include the University Hospital and The University of Texas Health Science Center at San Antonio. Equipment use for direct patient care will be in keeping with standards-of-care, without any additional equipment being required for the clinical research study.

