Data Collection: Data collection will include age, race, gender, BMI, data for calculating an APACHE II and SOFA scores, suspected source of infection, identified pathogens, pre-existing conditions that may predispose the patient to AF and the severity/classification of such illness (coronary artery disease, heart failure, chronic kidney disease, chronic obstructive pulmonary disease, diabetes mellitus); vital signs at the onset of AF (mean arterial pressure, systolic blood pressure, heart rate), lactate, pH, and serum bicarbonate at the time of AF onset; fluid resuscitation volume for the 24 hours prior to AF, vasopressor use (including drug, dose, duration) in the preceding 24 hours; other medications used to stabilize hemodynamic status in AF (e.g. β-blockers, calcium channel blockers, digoxin), other attempted methods of cardioversion attempted prior to amiodarone use (e.g. direct current cardioversion, other antiarrhythmic drug therapy); amiodarone loading dose, cumulative study amiodarone dose; the duration of time spent in AF before conversion to NSR, the incidence of AF recurrence; and hemodynamic variables to be assessed at various time points after the initiation of amiodarone (-6 hours, at onset of AF, 2 hours, 6 hours, 12 hours, and every 6 hours thereafter until day 7 or death)

including mean arterial pressure, central venous pressure, systolic blood pressure, heart rate, pH, serum bicarbonate, and serum lactate.

Monitoring for Efficacy and Safety:

Efficacy: Patients will be stratified based on response to therapy into one of three groups: conversion to NSR, nonconverting AF that is hemodynamically stable or non-converting AF that is hemodynamically unstable. The primary efficacy outcome is the mean heart rate every 6 hours after initiation of the amiodarone infusion to day 7 or death. Secondary efficacy endpoints will include the percentage of time spent hemodynamically unstable in the first 7 days following amiodarone initiation, intensive care unit length of stay (LOS), hospital LOS and 28-day mortality along with comparisons of the individual portions of the hemodynamic endpoints (MAP, HR, SBP), cumulative vasopressor doses of norepinephrine and vasopressin, CVP, conversion to NSR, maintenance of NSR, proportion of time spent in NSR after the start of the infusion to day 7 or death, pH, standard bicarbonate, serum lactate, and central venous oxygen saturation.

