Safety: Safety outcomes include worsening of hypotension (largely related to the rate of infusion and the polysorbate 80 diluent), bradycardia, acute elevations of liver function tests ≥ 3 times the upper limit of normal, phlebitis, QTc prolongation, skin reactions, neuropathy, and pulmonary toxicity. We will also collect premature study discontinuation due to any adverse event. Because the experimental group of this study is a partial load of amiodarone, rather than a full load, it is likely that the experimental group will experience fewer amiodarone related adverse effects than those receiving the current practice. In the setting of worsening hemodynamic stability during amiodarone infusion (i.e. SBP <90 mmHg OR MAP < 70 mmHg, despite HR control of < 120 bpm; need for fluid boluses ± vasopressors or dobutamine), which the medical team believes to be caused by IV amiodarone therapy:

- 1. the amiodarone infusion rate should be decreased by 50%, with efforts to increase back to the standard infusion rate after the patient is hemodynamically stable, *or*
- 2. switch from IV amiodarone to PO amiodarone therapy at a dose of 400 mg PO TID, or
- 3. emergent electro-cardioversion at the discretion of the medical team (as is the standard of care)

Data Analysis Plan: Data will be collected and stored using Microsoft Excel or Access. After data organization and cleaning, data will be imported into JMP 12.0 or SPSS. Data will be analyzed using both descriptive and comparative statistics. The primary outcome will be analyzed using repeated measures ANOVA. Nominal and ordinal variables will be compared using Chi-square test or Fisher's Exact test, as appropriate. Continuous variables will be tested for normality using the Shapiro-Wilk W goodness of fit test. Continuous variables with normal distributions will be compared using the student's t-test, while non-parametric variables will be compared using the Wilcoxon rank sum test. Statistical significance will be defined as an alpha level less than 0.05.

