All baseline demographics, including patient comorbidities, amount of fluid resuscitation, previous vasoactive therapies, and use of other interventions such as direct current cardioversion, will be entered into a multivariate regression model if the p value is less than 0.20 on univariate comparison between treatment groups. The multivariate regression model will be used to assess if baseline factors or previous treatment other than the intervention affected the study outcomes.

Based on extrapolation from available literature assessing HR control at 24 hours, we estimate that the full loading dose group will have a mean HR of 110 bpm over the course of 7 days, while the partial loading dose group will have a mean HR of 130 bpm over the course of 7 days. 7 day mean HR that is 20 bpm lower than the partial loading dose group. Therefore, we estimate that 250 patients will be necessary in each group to have an 85% power to detect a difference, assuming a 15% drop-out rate.

Item 7 Risks Section:

Complete the following table to describe the risks of all research procedures listed in Step 2, Institutional Form (items 28-34). Do not list risks of Routine care procedures here.

isks are described in the informed consent document – do not complete this table.

Research procedures	Risks
 example: History and physical Questionnaire Laboratory tests 	List the reasonably expected risks under the following categories as appropriate:
Add or delete rows as needed

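### A 20 bpm difference in 7-day mean heart rate does not require 250 patients per group: no SD is given, and a two-sided comparison of the means matches the stated figures only at an SD of about 69 bpm

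*Combined protocol and SAP*

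**What the plan says.** The closing paragraph of the Data Analysis Plan in Item 6 expects that the "full loading dose group will have a mean HR of 110 bpm over the course of 7 days" and that the "partial loading dose group will have a mean HR of 130 bpm over the course of 7 days". A sentence fragment then repeats the gap: "7 day mean HR that is 20 bpm lower than the partial loading dose group". The paragraph moves directly (with the word therefore) to the conclusion that "250 patients will be necessary in each group to have an 85% power to detect a difference, assuming a 15% drop-out rate". The only basis offered for the means is extrapolation from literature on heart rate control at 24 hours.

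Earlier in the same section the plan says: "The primary outcome will be analyzed using repeated measures ANOVA" and "Statistical significance will be defined as an alpha level less than 0.05". Item 6, Monitoring for Efficacy and Safety, defines the endpoint: "The primary efficacy outcome is the mean heart rate every 6 hours after initiation of the amiodarone infusion to day 7 or death".

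No heart-rate SD appears anywhere. Item 3 (Background) reports a fall from 150 to 104 bpm in one cited study without an SD. The SDs it does give concern amiodarone dose and treatment duration. Sidedness, the powered ANOVA effect and the within-patient correlation are not stated.

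**The concern.** A sample size for a difference in means depends on the ratio of the difference to the SD. The plan gives the difference, the power, the drop-out rate and the result, but not the SD. The missing SD can be solved for, and the value needed is far too large for a patient's 7-day mean heart rate.

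This paragraph is the only stated justification for enrolling 500 critically ill patients. As it stands, a reader cannot tell whether the trial is built to detect 20 bpm or something much smaller. At assumed SDs of 20 to 40 bpm, an observed difference of about 4 to 8 bpm would already reach p<0.05, well short of the 20 bpm on which the plan bases its size.

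**Working it through.** **Inputs from the documents (all Item 6, Data Analysis Plan).** Difference 130 − 110 = 20 bpm; power 85%; alpha 0.05; 250 per group, 1:1; drop-out 15%.

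**Inputs not in the documents.** The SD; the sidedness (two-sided taken as the main case, because the F test for group in an ANOVA has no direction); the powered effect (group difference in 7-day means taken as the main case, because the paragraph describes only that).

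**Step 1: try to reproduce 250.** It cannot be computed forwards without an SD, so invert the formula.
- Evaluable per group: 250 × 0.85 = 212.5
- z sum, two-sided: 1.960 + 1.036 = 2.996
- SD = 20 / (2.996 × √(2/212.5)) = 68.8 bpm (68.6 with the exact t)

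Forward check at SD 69: 214 evaluable, and 214/0.85 = 252 enrolled, which agrees with 250.

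| Reading | Implied SD (bpm) |
|---|---|
| Two-sided, 15% drop-out | 68.8 |
| Two-sided, no drop-out inflation | 74.6 |
| One-sided, 15% drop-out | 76.9 |
| One-sided, no drop-out inflation | 83.4 |
| 250 as trial total, two-sided, 15% drop-out (contradicts the text) | 48.6 |

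**Step 2: is 68.8 bpm credible?** Under a normal model:
- Below 0 bpm, given mean 110: Φ(−110/68.8) = 5.5%
- Above 220 bpm, given mean 130: 1 − Φ(90/68.8) = 9.5%

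Neither is believable for a 7-day average. If single six-hourly readings were modelled (28 per patient, compound symmetry), a patient-mean SD of 68.8 would need a single-reading SD of 68.8/√((1 + 27ρ)/28) = 121, 96, 82 and 72 bpm at ρ = 0.3, 0.5, 0.7 and 0.9. That is larger still.

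**Step 3: what 20 bpm would need, and what 250 would detect.** The SDs below are assumptions. Two-sided 0.05 throughout.
- Evaluable n per group = 2 × (2.996 × SD/20)², rounded up; enrolled = n/0.85, rounded up
- Detectable difference at 85% power = 2.996 × SD × √(2/212)
- Smallest significant observed difference = 1.96 × SD × √(2/212)

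| Assumed SD (bpm) | Evaluable per group for 20 bpm | Enrolled per group | Power for 20 bpm, 212 evaluable | Detectable at 85% power (bpm) | Smallest significant difference (bpm) |
|---|---|---|---|---|---|
| 20 | 18 | 22 | >99.9% | 5.8 | 3.8 |
| 25 | 29 | 35 | >99.9% | 7.3 | 4.8 |
| 30 | 41 | 49 | >99.9% | 8.7 | 5.7 |
| 40 | 72 | 85 | 99.9% | 11.6 | 7.6 |

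Even at SD 60, which is well beyond this range, 191 enrolled per group would be enough.

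**The case against.** **Another test may have been powered.** The plan names repeated measures ANOVA for a six-hourly outcome, and a group-by-time test can produce 250 at an ordinary SD. For example, assume 212 per group, 28 readings, SD 25, ρ = 0.5 and compound symmetry. Then 85% power needs a noncentrality of about 26, that is, a group difference that varies over time with an SD of about 1.7 bpm. This stands as a possible origin of the number, and it is why the finding is confined to a comparison of 7-day means. It does not rescue the paragraph, which states only two 7-day means: a constant 20 bpm gap produces no interaction at all.

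**A hidden allowance for override.** Item 6, Intervention, says "The primary attending or fellow physician may over-ride randomization", which would dilute the contrast. For 212 evaluable to have exactly 85% power, the 20 bpm contrast would have to shrink to the detectable difference. That is a loss of 1 − 5.8/20 = 71% at SD 20, and 64%, 56% and 42% at SDs 25, 30 and 40. The paragraph mentions no such allowance.

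**Deaths as loss.** A reader might infer from the 70–80% mortality in Item 3 that real loss far exceeds 15% and explains the 250. The documents do not support that. The figure is background mortality with no time frame, and the endpoint keeps readings up to death, so a patient who dies on day 3 still contributes a mean. Any calculation at 70–80% loss would be hypothetical, and it would contradict the stated 15%.

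**Dependence on assumed SDs.** This is a fair caution. Apart from the implied SD, the magnitudes are conditional illustrations. The direction is the same over the whole 20 to 40 bpm range.

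**Extraction damage.** One sentence is a fragment, but what remains restates the 20 bpm gap and nothing in it points to an SD.

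**Conclusion.** The point stands and should be fixed. For a two-sided 0.05 comparison of 7-day mean heart rate, the stated link between 20 bpm, 85% power and 250 per group is wrong at any plausible SD. It needs about 69 bpm (about 77 one-sided; about 75 two-sided without drop-out inflation). At assumed SDs of 20 to 40 bpm, 22 to 85 enrolled per group would suffice, and the planned size would detect about 6 to 12 bpm with 85% power.

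Three stronger conclusions are tempting but do not follow. The inputs are not algebraically contradictory; they agree, but only at an implausible SD. The trial is not shown to be underpowered: for this test at the stated 15% loss, the error is toward more patients than 20 bpm needs, and type I error is unaffected. Nor is it shown that 250 is enough for whatever the sponsor intended, because the SD and the powered effect remain unknown.

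**What to change.** Recompute and rewrite the sample size paragraph. State the SD of 7-day mean heart rate and its source, a two-sided alpha of 0.05, the ANOVA effect that is powered and, if single readings are modelled, the within-patient correlation. If any allowance for randomization override is built in, state that too.

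If 250 per group is kept, remove the claim that 20 bpm requires it. Replace it with the difference detectable at 85% power, for example: 212 evaluable per group (250 less 15%) give 85% power, two-sided 0.05, for a difference of about 7 bpm in 7-day mean heart rate, assuming an SD of 25 bpm [source]. Alternatively, state the actual power for 20 bpm. If the sponsor intended a group-by-time test, the paragraph should say so and give the assumed heart-rate profiles over time.

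The cost is one rewritten paragraph. If 250 is kept for a comparison of the means, the rewrite may also require an open statement that the trial is sized for a difference smaller than 20 bpm, which the sponsor would then need to justify. Whether enrolment should change can be judged only once the SD and the powered effect are stated.
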